2.15.2 Sample Size Rationale

Based on the need for data collected from this study, it was determined that a total of 50 subjects will be required, including departures.

2.15.3 Patient Populations

Interim results may be collected and reported. All data will be analyzed at the end of the study on a per device basis as well as overall. The primary analysis will be performed by the intention-to-treat approach. Everyone who begins the treatment is part of the study whether he or she completes the study or not. Additional per-protocol analysis may also be performed on subjects who complete the entire clinical trial according to the protocol. The most appropriate method of handling missing values will be chosen based on the individual trial goals, endpoints and context.

The analysis of demographic, medical history, and efficacy variables will be based on all patients who are randomized and receive at least one treatment. The analysis of safety data will be based on all patients who are randomized, receive at least one treatment, and have at least some safety data.

2.15.4 Analysis of Demographic and Medical History Variables

Summaries will be prepared for all important demographic and medical history variables. For quantitative variables summaries will include the sample size, mean, median, standard deviation, minimum, and maximum. For these variables the treatment groups will be compared using either a t-test or a Wilcoxon Rank Sum test, as appropriate. For categorical variables the summaries will include the sample size and the number and percent of patients for each outcome. For these variables the treatment groups will be compared using Fisher's Exact test. Statistical significance will be declared if the two-sided p-value is < 0.05.

2.15.6 Analysis of Safety Variables

Safety will be assessed through the degree of pain/discomfort related to the procedure (universal pain scale) and the collection of Adverse Events throughout the course of the study. For each treatment group these variables will be summarized. The summaries will include the number and percent of patients for each outcome. No statistical comparisons will be performed for any of these variables.

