2.10 Biopsy Portion of the Study

- Subjects may enroll in the biopsy portion of this study. If the subject has signed the biopsy consent form and enrolled, the following will also be performed:
 - Biopsies may be taken from a treated area the day of treatment and/or may be taken 1, 3, 7 (+/- 1 day), 14 (+/- 2 days), 21 (+/- 2 days), and/or 30 days (+/- 3 days) post last treatment. A control will also be taken on the contralateral side of the treatment area.
 - Biopsy subjects may receive up to 6 biopsies.
 - A local anesthetic, such as lidocaine, may be injected to the area prior to biopsy.

- A 2 mm or 3mm punch biopsy (based on Physician assessment) will be taken from the treatment area.
- Sutures may be used to close the incision site.
- The subject may be asked to attend a 1 week (7-14 days) post each biopsy visit to remove the sutures and assess side effects.
- The following post biopsy treatment instructions will be reviewed:
 - Slight redness, initial tenderness to the wound site is normal; however, if you experience more redness, swelling, pain, pus, or drainage contact the study site immediately.
 - If the biopsy site begins to bleed, apply direct pressure for 10-20 minutes. If it continues to bleed, call the study site immediately.
 - Keep the wound dry today and remove bandage in 24 hours and leave off.
 - Avoid hot tubs, pools, and ocean until sutures are removed. Avoid soaking in water until 14 days after your biopsy.
 - When showering, wash carefully and do not scrub or traumatize the treated skin, or allow spray of shower to strike the skin directly. If the skin is treated harshly, this can increase the risk of scarring.
 - After showering, lightly pat dry the wound or let it air dry, then cover the biopsy site with an application of Vaseline (or petroleum jelly) at least 1-2 times daily. Keeping the wound moist reduces infection, minimizes scarring, and prevents crust formation over the wound.
 - Band-Aids (or any generic Adhesive Bandages) may be used for sleeping or in daily routines where the area may be rubbed/irritated. Whenever possible, keep Band-Aid (or generic Adhesive Bandage) off of the area and keep the area moist with Vaseline (or petroleum jelly) as previously described but do not allow drying out and forming a hard scab.

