2.14 Adverse Event Recording

All data captured must be supported by the Investigator's timely assessment and documentation of the adverse event in the case report forms or source documents. All documented adverse events will be reviewed by the Sponsor or designee to determine whether the adverse event meets regulatory reporting requirements and to ensure timely adverse event reporting to meet local and global regulatory requirements. All adverse events must be followed until their resolution.

Adverse Events Pertaining to the SoftWave Device:

Potential adverse effects associated with shock wave treatments include those listed below:

- Transient moderate increase in pain
- Redness and swelling
- Hematoma and petechial hemorrhage
- Headaches and fainting during extracorporeal shock wave treatments
- Short-term hypoesthesia
- Nausea during therapy
- Tingling during therapy

Adverse Events Pertaining to the Marker:

Using a marker has minimal risks and may produce effects on the body such as redness or a rash.

Adverse Events Pertaining to Ultrasound Gel:

The gel is a water-based gel that may be placed on the skin during treatment. No known adverse events are documented. However, an allergic reaction is always possible when placing a topical gel onto the skin. Allergic reaction may include a mild reaction such as skin redness, irritation, or hives.

Biopsies

Complication with biopsies can include pain, redness, swelling, infection, bleeding, scarring and skin texture irregularities.

Lidocaine

You may experience pain and numbness at the site of the injection. You may also experience redness, rash, infection, skin damage or nerve damage at the site of the injection. You may experience temporary loss of sensation and muscle function at the site of injection.

1% lidocaine (Lidocaine) with Epinephrine Injection

Lidocaine with epinephrine contains the preservative sodium metabisulfite which may cause allergic-type reactions including anaphylactic symptoms such as itching, hives, swollen areas of the body, and/or trouble breathing and life-threatening or less severe asthmatic episodes in certain susceptible people.

Other Cautions:

Incomplete response or no response may occur since some subjects may not respond to treatment.

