2.15 Statistical Analysis**2.15.1 Hypothesis**

For this study to be considered a success, the average pain score is acceptable to the Physician as it relates to the type of treatment.

For additional objectives to be considered a success, the following criteria must be met:

- The side effect profile (adverse events) is acceptable to the Physician as it relates to the type of treatment.
- The subject satisfaction rates at the follow up visit will be $\geq 80\%$ (optional).
- Correct identification of pre-treatment images when compared to post treatment (30 and/or 90 day) images will be $\geq 80\%$ (optional).
- Successful collection of biopsies (optional).
- Successful collection of treatment assessment questionnaires (optional).

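### Adverse events are tabulated with no split by biopsy status, so the SoftWave side-effect profile shifts with the unfixed share of subjects who are biopsied

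*Combined protocol and SAP*

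**What the plan says.** All references are to the combined protocol and SAP.

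- **Safety summary (2.15.6).** "For each treatment group these variables will be summarized", and "The summaries will include the number and percent of patients for each outcome". No statistical comparison is planned.
- **Breakdown (2.15.3).** "All data will be analyzed at the end of the study on a per device basis as well as overall". The safety population is every treated subject with some safety data. Biopsy status is not mentioned.
- **Biopsy portion (2.10).** Participation is optional and no number of participants is set. "Biopsy subjects may receive up to 6 biopsies". Punches come from the treated area on the day of treatment or at set days up to day 30 after the last treatment, with a control on the contralateral side. Local anaesthetic, sutures and an extra visit after each biopsy, at which side effects are assessed, are all possible.
- **Expected reactions (2.14).** For the device the list includes a temporary increase in pain, and "Redness and swelling". For the punch: "Complication with biopsies can include pain, redness, swelling, infection, bleeding, scarring and skin texture irregularities".
- **Use of the result (2.15.1).** One success criterion reads: "The side effect profile (adverse events) is acceptable to the Physician as it relates to the type of treatment".
- **Causality (14.0).** Each event is rated on five levels for its relationship to the study device. There is no rating against the biopsy procedure.

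**The concern.** The adverse event table is meant to describe what SoftWave does to subjects. In a biopsied subject, some local reactions will come from a punch, an injection or a suture, and three of the listed reaction types (pain, redness, swelling) are shared with the device. Biopsied subjects may also have extra visits at which side effects are looked for, so events are sought more often in them.

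The share of subjects biopsied is left open, so a percentage over all subjects mixes two procedures in a proportion that the plan does not control. The acceptability criterion in 2.15.1 has no numerical limit, which leaves this table as the evidence for the judgement. The mixing can work in two directions. Punch reactions can inflate the apparent device rate, or real late device reactions can be put down to the punch.

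**Working it through.** **The plan's own figure.** The only number is the sample size: "it was determined that a total of 50 subjects will be required, including departures" (2.15.2). It comes with no event rate, effect size, alpha or power, so it cannot be reproduced. It serves here only as a denominator.

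**Inputs for the illustration**
- From the documents: 50 subjects; share biopsied *f* not fixed; biopsies per biopsied subject *k* at most 6.
- Assumed, because no rates are given: share of subjects with a local reaction to the device, *d* = 10%, 20% or 40%; chance of a like reaction per biopsy, *b* = 10%, 30% or 50%; independence between the two.

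**Formula.** Share of all subjects with a local reaction = *d* + *f* (1 − *d*) [1 − (1 − *b*)^*k*].

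**Central case**, *d* = 20%, *b* = 30%, *k* = 1, *f* = 40%: 0.20 + 0.40 × 0.80 × 0.30 = 0.296. In subjects, 10 of 50 react to the device and a further 20 × 0.80 × 0.30 = 4.8 react only to the punch, so 14.8 / 50 = 29.6%.

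**Range**

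| *d* | *b* | *k* | nobody biopsied | 40% biopsied | all biopsied |
|---|---|---|---|---|---|
| 40% | 10% | 1 | 40% | 42.4% | 46% |
| 20% | 30% | 1 | 20% | 29.6% | 44% |
| 20% | 30% | 6 | 20% | 48.2% | 90.6% |
| 10% | 50% | 6 | 10% | 45.4% | 98.6% |

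The first and last rows are the smallest and largest shifts over the assumed grid. In every row the device rate is constant. Under these assumptions the non-biopsied subjects estimate *d* whatever *f* is.

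**Does the relationship rating remove the mixing?** Setting 14.0 beside 2.15.6:
- The two lowest levels allow for other therapeutic interventions, so some punch reactions can be rated away from the device.
- The middle level admits events that fit a known response to sampling sessions. This may be template wording, but biopsy is the only tissue sampling here, so a punch reaction can be rated as possibly device-related.
- 2.15.6 plans no table by relationship, so the rating does not reach the reported percentages.

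**Precision after a split.** Exact 95% intervals for an observed 20%: 10.0–33.7% with 50 subjects, 7.7–38.6% with 30, 5.7–43.7% with 20. If 40% were biopsied, 30 of the 50 would be non-biopsied.

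**The case against.** The best defence is that the mixing is inferred from silence. Section 2.15.6 does not say that punch reactions count as SoftWave effects, and the documents contain several means of telling them apart:
- **Timing.** Section 2.1 places biopsies after the final treatment, so most treatment-phase reactions come before any punch, and several listed device effects are short-lived.
- **Type.** Infection, scarring and texture irregularities are listed only for biopsies.
- **Control.** The contralateral punch gives a within-subject reference.
- **Rating.** Every event is assessed individually against the device.

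In addition, no numerical rule depends on the percentage, and 2.10 describes slight redness and early tenderness at the wound as normal, so some punch reactions may never be recorded as adverse events.

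Much of this stands as a limit on size. It does not remove the point, because none of these separators is used in the planned tables.

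A reader might infer more than the documents support:
- *That all 6 biopsies are in treated skin.* Six is a ceiling, and it may include the contralateral control.
- *That the two procedures cause the same reactions.* The overlap is partial.
- *That the relationship rating is useless.* It helps in part.
- *That biopsy lowers satisfaction and so biases the 80% criterion.* Wounds or scars could plausibly matter at 30 and 90 days, but nothing in the documents shows that they do. The content of the satisfaction question is not given, and the criterion is optional.

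**Conclusion.** The point holds for adverse events. As planned, the percentage of subjects with pain, redness or swelling depends on how many are biopsied, a number that the plan leaves open, and the causality rating does not correct this because it has no biopsy category and is not tabulated.

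The size cannot be stated from the documents. On assumed rates of 20% for the device and 30% per biopsy, one biopsy each, having 40% of subjects biopsied moves the figure from 20% to 29.6%. On the mildest assumptions examined it moves only from 40% to 46% even if everyone is biopsied. All of these figures rest on assumed rates and independence.

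The primary result is largely unaffected, because the discomfort score is taken at treatment visits and biopsies mainly follow the last treatment. For satisfaction, the documents support no more than a sensitivity display.

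**What to change.** In 2.15.6:
1. Tabulate adverse events separately for non-biopsied and biopsied subjects.
2. In biopsied subjects, show events before and after the first biopsy in separate columns, by site (treated area, punch site, contralateral control) and by relationship to the device and, as an added rating, to the biopsy procedure.
3. Base the SoftWave percent-of-patients figures on non-biopsied subjects with full follow-up. Report pre-biopsy events in biopsied subjects alongside, with their shorter observation time.
4. Do not pool these two sets into one percentage. Follow-up cut at the first biopsy misses late device reactions, and the pooled figure would again depend on the share biopsied. For example, with an assumed true rate of 30%, half of it occurring before the first biopsy, and 40% of subjects biopsied: 0.6 × 30% + 0.4 × 15% = 24%.
5. Keep the overall table so that no event is dropped.

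With the satisfaction analysis, show the rate with and without biopsied subjects, labelled as a sensitivity display.

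The cost is SAP wording, extra table columns, and case report form fields for biopsy date, event site and relationship to the biopsy where these are not already collected (the forms are not in the documents). The statistical cost is smaller subgroups with wider intervals, as shown above. No test loses power, since none is planned for these variables.

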2.7 Treatment Procedures

- Procedures for the shock wave treatment:
 - The defined study area will be identified and will be cleansed thoroughly using a facial cleanser or mild soap and water. The treatment area may be marked with a marker.
 - The device may be used in accordance with the Protocol Manual and Instructions for Use.
 - Test spots may be performed prior to treatment in an area, such as on the hand, or in or close to the treatment area or so the subject can get used to the sensation.
 - Ultrasound gel will be applied to the area to be treated.
 - The applicator will be placed on the skin and slowly moved over the identified treatment area administering pulses of acoustic pressure shockwaves.
 - Parameters may be adjusted throughout the treatment to increase subject comfort.
 - Subjects will be asked to report the general level of treatment discomfort/pain on a scale of 0 (none) to 10 (maximum intolerable pain).
 - Parameters and tissue response will be continuously monitored and recorded during treatment.
- The additional treatments will follow the same procedure.
- Subjects and Clinicians may be asked to complete treatment questionnaires.
- Subjects may receive up to 5 treatments. Treatments will be performed every 3 – 14 days.

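### Adverse events are to be summarised per patient with no session count, so risk cannot be separated from number of sessions and comparability of the per-device tables is not assured

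*Combined protocol and SAP*

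**What the plan says.** Section 2.15.6 (Analysis of Safety Variables) covers pain and adverse events. It states "For each treatment group these variables will be summarized", then "The summaries will include the number and percent of patients for each outcome", and closes with "No statistical comparisons will be performed for any of these variables". No event count, rate per session, table of exposure or breakdown by number of sessions is specified anywhere.

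Exposure is open. Section 2.7 says "Subjects may receive up to 5 treatments. Treatments will be performed every 3 – 14 days", and under section 2.15.3 one treatment is enough to enter the safety set. Section 2.1 allows a subject also to be treated with a similar shockwave device. Neither the number of sessions with that device nor their order is given. Section 2.15.3 adds "All data will be analyzed at the end of the study on a per device basis as well as overall".

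Among the success criteria for the additional objectives, section 2.15.1 lists: "The side effect profile (adverse events) is acceptable to the Physician as it relates to the type of treatment". It gives no numerical limit.

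Adverse events are documented after treatment (section 2.8), and the visit schedule in section 2.13 marks their assessment at every treatment visit.

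**The concern.** Many of the device effects listed in section 2.14, such as redness and swelling, petechial hemorrhage, and nausea or tingling during therapy, are acute and can occur afresh at each session. A patient treated five times has five chances to be counted and a patient treated once has one. The percent of patients therefore mixes two quantities: risk per session and number of sessions.

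Two uses of the table are exposed. The first is the set of per-device descriptive tables. If sessions per subject happened to differ between devices, two devices with equal risk per session would show different percentages. The second is the Physician's judgement of the side effect profile. A high percentage could reflect a less well tolerated treatment or only a longer course, and a low one could reflect early stopping. Section 2.1 (Predictive power) then treats an acceptable side effect profile as the premise for expecting results in other marketable indications.

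**Working it through.** The plan states no adverse event rate, so there is no figure to reproduce. The check asks how far the planned statistic moves when only the number of sessions changes.

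**Inputs from the documents**
- Sessions per subject, m: 1 (minimum for the safety set, 2.15.3) to 5 (maximum, 2.7).
- Spacing of 3 to 14 days (2.7); follow-up at 30 and 90 days after the last treatment (2.9).
- Up to 50 subjects in total (2.1, 2.15.2), with no split by device or number of sessions.

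**Assumptions, not in the documents**
- Risk of an event per session, p: 2% to 20%.
- Within-patient correlation between sessions, ρ: 0 to 1.

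**Step 1: independent sessions.** P(at least one event) = 1 − (1 − p)^m. For p = 10% and m = 5 this is 1 − 0.9^5 = 41.0%.

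| Risk per session | 1 session | 3 sessions | 5 sessions | Ratio, 5 to 1 |
|---|---|---|---|---|
| 2% | 2.0% | 5.9% | 9.6% | 4.8 |
| 5% | 5.0% | 14.3% | 22.6% | 4.5 |
| 10% | 10.0% | 27.1% | 41.0% | 4.1 |
| 20% | 20.0% | 48.8% | 67.2% | 3.4 |

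**Step 2: correlated sessions.** Use a beta-binomial with a = p(1 − ρ)/ρ and b = (1 − p)(1 − ρ)/ρ. Then P(at least one event) = 1 − ∏ (b + i)/(a + b + i), with i from 0 to m − 1. For p = 10% and m = 5:
- ρ = 0: 41.0%, as above.
- ρ = 0.2 (a = 0.4, b = 3.6): 1 − 0.900 × 0.920 × 0.933 × 0.943 × 0.950 = 30.8%.
- ρ = 0.5 (a = 0.1, b = 0.9): 1 − 0.900 × 0.950 × 0.967 × 0.975 × 0.980 = 21.0%.
- ρ = 1: 10.0%. The same patients react every time, and the number of sessions has no effect.

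**Step 3: the two denominators side by side.** Take two groups of 25 subjects with p = 10% and independent sessions, one group treated five times and the other once.
- Percent of patients: 25 × 0.410 = 10.2 of 25 (41%) against 2.5 of 25 (10%).
- Percent of sessions: 12.5 of 125 (10%) against 2.5 of 25 (10%).

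The session denominator recovers the common risk and the patient denominator does not.

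**Step 4: observation time.** Follow-up runs from the last treatment, so it too lengthens with the number of sessions. From first treatment to the 90-day visit is 90 days with one session, and 90 + 4 × 3 = 102 to 90 + 4 × 14 = 146 days with five.

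**Step 5: can recurrent events be counted?** Section 14.0 says that events are captured throughout the study. It also says that once study-associated events have resolved, no further adverse event reports will be made for that subject. Read literally, the second statement would drop new events at later sessions. The two statements conflict.

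**The case against.** Several points on the other side stand.

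- A reader might infer that the plan permits only percent of patients. It does not go that far: section 2.15.6 says what the summaries will include, which does not exclude others. What remains is that no other is specified.
- A reader might infer that the devices cannot be compared. That follows only if sessions per subject differ by device, and nothing in the documents says they will. The comparison device is itself optional (section 1.2).
- No formal safety comparison is planned and no numerical limit is set, so no test is distorted and no threshold is crossed. The harm is to interpretation. Since descriptive tables are the only safety analysis planned, that still matters.
- The size rests on assumed p and ρ, and the effect vanishes at ρ = 1.
- Percent of patients answers a proper question, namely how many people are affected over a course. A reader might infer that the rate per session should replace it as the basis for the side-effect judgement, but that rate can mislead too. Suppose that 10 of 50 subjects react at session 1 and stop, and 40 have five event-free sessions. Then 10/50 = 20% of patients are affected, but the rate per session is 10/(10 + 40 × 5) = 10/210 = 4.8%. Neither figure is sufficient alone.
- With at most 50 subjects, modelled intervals by event type, device and session number would rest on many sparse or empty cells.

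None of this removes the gap: the plan has no exposure denominator, and no rule for a subject treated with both devices.

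**Conclusion.** The concern holds in a limited form. The only adverse event summary specified is per patient, exposure may run from 1 to 5 sessions, and sessions per subject and device are neither fixed nor reported. At an assumed 10% risk per session, the planned percentage after five sessions is between 1 and 4.1 times that after one, depending on within-patient correlation. It is 3.1 times at a correlation of 0.2 and 2.1 times at 0.5. Only perfect correlation removes the dependence.

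It follows that comparability of the per-device tables is not assured, and that the Physician cannot separate higher risk from more sessions. The documents do not show that the devices will in fact differ in exposure, that a formal result is affected, or that percent of patients is an improper statistic.

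**What to change.** Keep the number and percent of patients in section 2.15.6 and add beside it, not in its place:

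1. The distribution of sessions delivered, per subject and per device.
2. Sessions with a new treatment-related event divided by sessions delivered, by device. Give a 95% interval clustered on subject for the overall rate per device, and simple counts without modelling by event type and session number.
3. A rule assigning each event to a session and a device, including for subjects treated with both. Tabulate biopsy and lidocaine events separately, since they do not arise from a shockwave session.

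State in section 2.15.1 that both summaries inform the side-effect judgement. Reconcile the two statements in section 14.0 so that events at later sessions are recorded and counted.

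The cost is one extra descriptive table and an attribution rule to be agreed before analysis. Adverse events are already assessed at each treatment visit, so no new visits are needed, and the sample size does not change.
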